2.1 Objectives & Hypotheses

	
at arrival ,15, 30, 60, and 90 minutes during Post-Operative Care Unit stay.
 
 - Proportion of patients who have a surgical conditions score in each category (Excellent, good, fair and poor). 
 • Surgical conditions will be rated using a four-point surgical rating scale (SRS) by an anesthesiologist. (not attending physicians) every 15 minutes and every change seen or surgeon's complaint. • The SRS will be also rated by an expert anesthesiologist and expert ENT surgeon from VDO recorder every change seen at a vocal cord. -To assess intubating condition in patients who has endotracheal insertion. This will be assessed by anesthesiologists right after finishing intubation.. 
2.1.2 List the clinical hypotheses.
 
 1. Sustained deep NMB for the duration of surgery in patients undergoing Endolaryngeal Procedures has better surgical conditions compared to those receiving moderate NMB when rated using a four-point surgical rating condition scale (SRS). 2. The frequency of Clinical Signs of Early recovery during an Endolaryngeal Procedures are less frequent in the Deep NMB group compared to the Moderate NMB.

2.2 Background & Rationale, Significance of Selected Topic & Preliminary Data
	
Neuromuscular Blocking (NMB) agents are routinely prescribed in patients who undergo an Endolaryngeal Procedures. Ideally, these Procedures require a short duration of NMB since they are short and fast operations. Sometimes, they may also finish unexpectedly. In Thailand, a short acting NMB is unavailable. The use of intermediate NMBs has many concerns. During the maintenance phase for patients undergoing an Endolaryngeal Procedures under general anesthesia, additional boluses of an NMB agent occurs only in response to Surgeon complaints regarding muscle tension. The main contributing factor is that further doses of muscle relaxants may cause unacceptable delays to extubation.
 
Secondly, there is a lack of data supporting the use of sustained deep NMB throughout Endolaryngeal Procedures.
 
To maintain the same level of stillness, patients without NMB required more anesthetic than patients treated with NMB.¹ A study found that 16 of 19 (84%) patients had hypopnea or apnea after a manually controlled continuous infusion of 0.125 mg/kg/min remifentanyl for 2 minutes followed by a continuous infusion of 0.05 mg/kg/min remifentanyl.² Another study examined the combined effect of propofol and remifentanyl and concluded that their effect on respiration was strikingly synergistic, resulting in severe respiratory depression.³ These data has shown that NMB is required in Balance Anesthesia.
 
Given these considerations, we will conduct a randomized, open-label trial aiming to compare two treatment strategies; Deep neuromuscular Blockade (TOF 0, PTC 1-2) and moderate Neuromuscular Blockade (TOF 1-2) by using Rocuronium 0.6 mg/kg⁴ and 0.4 mg/kg^{5,6} in deep NMB group and moderate NMB group, respectively, as intubation doses. Usually, neuromuscular block sufficient for intubation is about 80% block or greater. The ED95 is defined as a dose required to produce 95% suppression of the first [T1]⁷. In this study, after patients are given rocuronium dose at 0.4 mg/kg (1.3 x ED95) in moderate group and 0.6 mg/kg (2 x ED95) in deep block group, the endotracheal tube will be inserted following the maximal depression T1^{6,8}. Since the maximal depression T1 function cannot be expressed on TOF watch, TOF count can be substituted. Twitches suppression of 90% would equate to a TOF

count of 1 or less⁹ (more detail in exhibit A). We hypothesize that deep NMB will offer better surgical conditions. We will also descriptively examine whether the two dose levels of Sugammadex as the reversal agent will provide similar (between the moderate and deep block groups) time of readiness to discharge from Operating room and PACU, which are defined by train of Four ratio > 0.9 and by Modified Aldrete's score ≥ 9 . Consequently, patients would be safely discharged.

2.3 Study Design

Protocol overview:

We will conduct a multi-center, open-label, assessor-blinded, randomized, parallel intervention trial at University Hospitals in Thailand. The eligible subjects will be randomly allocated to either the deep neuromuscular block group or moderate neuromuscular block group. Details of intervention will be explained in the next section (treatment protocol). Clinical response will be evaluated.

[figure not shown]
Inclusion criteria:

1. Male or female aged 18 – 60 years; ASA I-III.
2. Subjects have been planned for elective endolaryngeal. Procedures (Direct Laryngoscopy with laser (micro-)surgery in patients with endolaryngeal lesions

Exclusion criteria:

1. Any renal impairment (CrCL < 80 ml/ min)
2. Any hepatic impairment; Child Pugh A, B or C
3. BMI > 30 kg m2
4. Known or suspected generalized neuromuscular disorders
5. Allergies to Rocuronium, Sugammadex, Sevoflurane, Propofol, fentanyl used during general anesthesia
6. Hypersensitivity to the active substance or to any of the excipients
7. Female patient who are pregnant and breastfeeding.
8. Patient with poor Glasgow Coma Score and mental derangement who is unable to give informed consent.
9. Patient with Tracheostomy tube.

2.4 Study Flowchart

[figure not shown]

Figure 10
Study flow chart (please see last page)

2.5 Study Procedures

All eligible subjects will be identified through hospital admission for Endolaryngeal Procedures database on daily basis. The investigator will obtain documented consent from each potential subject. Consent must be documented by the subject's dated signature on a consent form along with the dated signature of the person conducting the consent discussion. Depending on local law or review committee requirements such consent may also need to be signed by an impartial witness.

Treatment allocation:

The eligible subjects will be allocated to each study group by randomization. The randomization will be performed by computer-generated block randomization algorithm with allocation concealment. The randomization will be stratified into "Anesthetic Procedures with endotracheal tube" and Anesthetic Procedures without endotracheal tube.

Perioperative protocol:

All patients received balance anesthesia with Propofol, Fentanyl and Rocuronium agents. During the Procedures, routine monitoring is applied [electrocardiography, arterial blood pressure, heart rate, electroencephalographic monitoring, pulse oxymeter)

Study intervention:

1. Deep Neuromuscular blockade group:

- After the enrollment Following induction with Targeting propofol concentrations (TCI) of 4 to 4.5 µg/mL, single bolus injection Fentanyl of 1-2 µg/kg, and single bolus injection rocuronium⁴ of 0.6mg/kg will be administered. When following maximal depression of T1 or TOF count 1^{6,9} endotracheal insertion will be initiated in anesthetic procedures with endotracheal tube. Choices of other induction anesthetic agents except NMB agent are at the discretion of the attending anesthesiologist.
- During maintenance phase, if recovery after 1 Post-Tetanic-count (PTC) responses, a continuous infusion can be initiated to maintain deep NMB (TOF =0, PTC 1-2). The initial pump rate will be set at 0.5 mg/kg per hour. The pump rate could be increased or decreased to keep the target TOF and PTC.
- During maintenance phase, Fentanyl 0.5 ug/kg may be administered when SBP or HR increase by 10%, as well as, Target propofol concentrations of 3

to 6 µg/mL usually maintain satisfactory anaesthesia.

- Electroencephalographic monitoring using either bispectral index (BIS) module system or Spectral Entropy is mandatory. BIS value is within the range of 40–60. The recommended range of reaction entropy (RE) and state entropy (SE) is 40–60 in appropriate anesthesia depth, which is identical to that of BIS.
- **Deep** NMB should be maintained throughout the operation.
- At the end of surgery, continuous infusion Rocuronium and Propofol are discontinued and paralysis will be simultaneously reversed by Sugammadex 4mg/kg from PTC 1-2.
- TOF will be monitored every 15 seconds. The PTC will be recorded one minute after disappearance of single twitch¹⁰. PTC will be monitored every 6 minutes^{10, 11} during surgery. When it is required TOF during emergence phase until patients discharge from PACU., it will be monitored every 15 seconds during emergence phase, at 1,3,5,10, 15 and subsequently every 5 minutes after extubation until arrive PACU, and every 15 minutes at PACU arrival time until patients discharge from PACU.

2. **Moderate Neuromuscular blockade group:**

- After the enrollment, following induction with Targeting propofol concentrations (TCI) of 4 to 4.5 µg/mL, single bolus injection Fentanyl of 1-2 µg/kg, and single bolus injection rocuronium of 0.4mg/kg^{5,6} will be administered. When following maximal depression of T1 or TOF count 1^{6,9}, endotracheal tube will be initiated in anesthetic procedures with endotracheal tube. Choices of other anesthetic agents except NMB agent are at the discretion of the attending anesthesiologist.
- During maintenance phase, if recovery at the presence of <10% of control T1 of TOF from initial doses of 0.4 mg rocuronium, a continuous infusion can be initiated to maintain TOF = 1 – 2. The initial pump rate will be set at 0.5 mg/kg per hour.
- During maintenance phase, Fentanyl 0.5 ug/kg may be administered when SBP or HR increase by 10%, as well as, Target propofol concentrations of 3 to 6 µg/mL usually maintain satisfactory anaesthesia. Electroencephalographic monitoring using either bispectral index (BIS) module system or Spectral Entropy is mandatory. BIS value is within the range of 40–60. The recommended range of reaction entropy (RE) and state entropy (SE) is 40–60 in appropriate anesthesia depth, which is identical to that of BIS.
- **Moderate** paralysis should be maintained throughout an operation.
- Continuous infusion Rocuronium and Propofol are discontinued at the end of surgery. Reversed the paralysis by Sugammadex 2 mg/kg will be administered at reappearance of T2.
- TOF will be monitored every 15 seconds during intraoperative¹⁰ and during emergence phase. It will be at 1,3,5,10,15 and subsequently every 5 minutes after extubation until arrival PACU and every 15 minutes at PACU arrival time until patients discharge from PACU.

Dosages of anesthetic agents:

At induction phase: Premedication with midazolam 1-2 mg single intravenously bolus could be administered at physician discretion.

1. **Rocuronium**⁴ will be given at an initial dose of 0.6 mg/kg in Deep NMB group and 0.4 mg/kg at induction phase; with these doses, patients could obtain adequate intubation conditions. Following maximal depression of T1 or TOF count 1^{6,9}, endotracheal tube will be initiated in anesthetic procedures with endotracheal tube.

2. **Propofol** will be given administered with the assistance of a Target Controlled Infusion (TCI) system. In adult patients under 55 years of age anaesthesia or ASA I-II can usually be induced with target propofol concentrations of 3.5 to 4.5 µg/mL. Induction time with these targets is generally within the range of 60 to 120 seconds.

A lower initial target concentration should be used in patients over the age of about 55 years or in patients of ASA grades III.

3. **Fentanyl** will be at the discretion of the attending anesthesiologist and is administered in single bolus injection of 1 to 2µg/kg.

At Maintenance phase:

1. **Rocuronium:** The initial pump rate will be set at 0.5 mg/kg per hour.
 - **Deep NMB:** After initial doses of 0.6 mg Rocuronium, a continuous infusion can be initiated to maintain 0 responses to train-of-four (TOF) stimulation or 1-2 responses to Post-Tetanic Count (PTC) (Deep NMB). The pump rate will vary and depends on the PTC value. The initial pump rate will be set at 0.5 mg/kg per h. In case of a deviation from the required PTC value the pump rate can be increased or decreased. This was left to the discretion of the attending anaesthetist.
 - **Moderate NMB:** After evidence of early spontaneous recovery (< 10% of control T1) from initial doses of 0.4 mg rocuronium, a continuous infusion can be initiated to maintain 1 to 2 responses to train-of-four stimulation (Moderate NMB). The initial pump rate will be set at 0.5 mg/kg per h. In case of a deviation from the required TOF value the pump rate can be increased or decreased. This was left to the discretion of the attending anaesthesiologist.
2. **Opioid :**Fentanyl 0.5 µg/kg will be administered when SBP or HR increase by 10%. If there was persistent increase SBP or HR after administration of Fentanyl 0.5 µg/kg, the subsequent dose of Fentanyl may be administered at the discretion of the attending anesthesiologist.
3. **Propofol:** Target Propofol concentrations of 3 to 6 µg/mL usually maintain satisfactory anesthesia.

At emergence phase:

1. **Sugammadex**¹³ will be given 4 mg/kg at the end of surgery, which is from deep NMB (PTC = 1-2) or 2 mg/kg if spontaneous recovery has occurred up to at least the reappearance of T2
2. **Intravenous agents** will be stopped at the discretion of attending anesthesiologist.
3. **Extubation** when TOF is ≥ 0.9.

Withdrawal or Termination from Study:

Subjects may withdraw at any time or be dropped from the study at the discretion of the investigator should any untoward effects occur, such as hypersensitivity.

2.6 Study Duration	
The total study duration is 16 months (4 months of institutional review board submission/approval, 8 months of recruitment, 3 months of study analysis and reporting)

2.7 Statistical Analysis and Sample Size Justification	
The principle investigator will be responsible for analyzing the study data. Since the research team is not blinded to the muscle relaxant used and the level of NMB, either the attending anesthesiologist or the research assistant is responsible for both the administration of the muscle relaxant and the degree of NMB. The attending anesthesiologist is also not blinded. He or she will not discuss the NMB with the surgeon or the research team. After the surgery has finished, subjects who receive rocuronium will be reversed with sugammadex 4 mg/kg or 2 mg/kg. Again, this will be known by the attending anesthesiologist only and will be blinded to surgeon and Anesthesiologist and Otolaryngologist Experts who will rate the surgical conditions..
 
Variables/Time Points of Interest:
 
1. Primary outcome:
 
1) Proportion of patients who have a surgical conditions score of excellent,
 
 • Surgical conditions will be rated using a four-point surgical rating scale (SRS) by the Surgeon right after operation. • The SRS has been modified from Intubating score¹⁰. • There are three variables, which are ease of laryngoscopy, condition of the vocal cords and the Reaction to insertion of the endoscopic tube and cuff inflation. These are scored on a four-point scale (0-3) and the total score is a sum of each component to give an overall Surgical Conditions score for each patient. • The assessment is based on the time point right after operation. • A total score of 8-9 was considered excellent, 6-7 good, 3-5 poor and 0-2 bad; good and excellent were taken as clinically acceptable. 
2. Secondary outcomes:
 
1) Proportion of patients who are ready to be discharged from post-operative care, defined as Modified Aldrete's score ≥ 9, at 0,15, 30, 60,90 minutes after reach of TOF > 0.9.
 
 • Modified Aldrete's score: A score ≥ 9 is required for discharge. 
2) Proportion of patients who are ready to be discharged from operating room, defined as TOF > 0.9 at time of tracheal Extubation, 1,3,5, 10 minutes after finish of a procedure.
 
3) Frequency of clinical signs of early recovery during Endolaryngeal Procedures.

Clinical signs of early recovery:

- 1) Airway pressure alarm
- 2) Movement of Vocal cords on Laryngeal Video monitor
- 3) Movement of the abdomen
- 4) Change of End Tidal CO₂

3. Other outcomes:

- 1) Proportion of patient at risk of of Post-Operative Residual Curarization (PORC) (TOF ration < 0.9) at 1,3,5,10 minutes after finish of a procedure and at 0, 15,30, 60, 90 minutes during Post-Operative Care Unit stay.
- 2) Time to readiness to discharge from Post-operative Care Unit which is time from Post-operative Care Unit (PACU) admission to reach “acceptable” score of Post-operative discharge score.
- 3) Time readiness to discharge from operating room, which is time from finish of procedures to train of Four ratio > 0.9
- 4) Proportion of patients who have a surgical conditions score in each category (Excellent, good, fair and poor).
 - Surgical conditions will be rated using a four-point surgical rating scale (SRS) by an anesthesiologist. (not attending physicians) every 15 minutes and every change seen or surgeon’s complaint.
 - The SRS will be also rated by an expert anesthesiologist and expert ENT surgeon from VDO recorder every change seen at a vocal cord.
- 5) Intubating condition in patients who has endotracheal insertion. This will be assessed by anesthesiologist right after finishing intubation by using the same score of endolaryngeal surgical condition

Study Variables during anesthesia

Endolaryngeal surgical condition¹⁰:

During the endolaryngeal Procedures, a surgeon scores the surgical working conditions right after the end of procedures. We adapted the Intubation Condition criteria^{11,12} included three variables:

- 1) jaw relaxation and resistance to laryngoscopy blade (laryngoscopy component)
- 2) the position and movement of vocal cords (vocal cord component)
- 3) coughing (reaction to endolaryngeal and endobroncheal Procedures component)

Evaluation of Endolaryngeal/Endobroncheal surgical conditions¹²

Variable assessed	Clinically acceptable		Not clinically acceptable	
	Excellent = 3	Good = 2	Poor = 1	Impossible = 0

Laryngoscopy[‡] 
 • Jaw relaxation • Resistance to blade 	Easy 
 • Relaxed • None 	Fair 
 • Not fully relaxed • Slight 	Difficult 
 • Poor relaxation • Active 	Impossible 
 • No relaxation
Vocal cord 
 • Position • Movement 	
 • Abducted • None 	
 • Intermediated • moving 	
 • Closing 	
 • Closed
Reaction to insertion of the endoscopic tube and cuff inflation 
 • Diaphragmatic movement • coughing 	
 • None • None 	
 • Slight^β movement • None 	
 • Vigorous movement^θ • Sustained coughing^θ 	
 • Bucking • Severe coughing

‡Laryngoscopy

Easy: jaw relaxed, no resistance to blade insertion

Fair: jaw not fully relaxed, slight resistance to blade insertion

Difficult: poor jaw relaxation, active resistance of the patient to laryngoscopy.

β One to two weak contractions or movement for less than 5 s.

θ More than two contractions and/or movement for longer than 5 s.

Endolaryngeal surgical site conditions⁹:

Excellent ;Score = 8-9

Good ;Score = 6 -7

Fair ;Score = 3-5

Poor ;Score =0-2

Surgical rating

During the laryngoscopic Procedures, the surgical condition is scored by the surgeon using a four-point SRS right after the Procedures. To reduce variability in the surgical rating, all surgeries are performed by a single surgeon at each institute.

The surgical rating scores (SRS) condition at 15-minute intervals will be recorded and rated by an anesthesiologist during the Procedures. In case of a sudden change in surgical conditions, additional scores are obtained. If conditions are poor (score 0 or 2), muscle relaxation is increased according to protocol.

Before commencing the study, both the surgeon and the anesthesiologists will receive training in how to use and implement the specific study Procedures and how to rate the surgical condition score.

Moreover, the first five Procedures performed in conformance with this protocol will not be used for data analysis; thus, the Procedures will be practiced five times before data collection starts.

Intubation score

At the end of intubation, the intubation condition is scored by anesthesiologist by using the same score of endolaryngeal surgical condition

Video images

The video images will be collected from the camera connected to endoscope placed

above vocal cord or field of the surgery. The images collected will be the images of Video monitor used by the surgeon to observe the surgical field throughout the Procedures. Variables that could not be captured by VDO recoder i.e. patients' reaction intra-operative, coughing, bucking, diaphragm movement and either physician's complaint of tightness/non-relaxation or request more relaxation agents will be recorded by anesthesiologist in the theater.

Thus, the collected video images are identical to the image of the surgeon during the Procedures as well as should be included surgical condition related-events occurs interoperations.

The videos will be rated by a surgical expert (one Ear-Nose-Throat surgeons with expertise in laryngoscopic Procedures) and an anesthesiologist (with expertise in giving anesthesia for laryngoscopic Procedures). These experts are blinded to the level of NMB and have no knowledge of the study endpoints. The rating score will be identical to the surgical rating score. All changes will be recorded.

Monitoring¹⁰:

Neuromuscular function using an acceleromyograph measured at the wrist (TOF-watch SX[®]). The TOF-watch generates an electrical stimulus to the ulnar nerve and measures contractions of the adductor pollicis muscle (causing adduction of the thumb) through a sensor attached to the tip of the thumb. The thumb is placed in a flexible adaptor that applied a constant preload to the thumb. Before administration of the NMB agent, the device is calibrated according the specifications of the manufacturer. To that end, before administration of the neuromuscular blocking agent after induction of general anesthesia, the following Procedures are conducted to standardize the neuromuscular monitoring: (i) application of a tetanic ulnar nerve stimulation (50 Hz for 5 s); (ii) calibration of the TOF watch; and (iii) performing a series of TOF measurements ensuring that the TOF ratio differs by <5% between measurements. If the TOF ratio differed by >5% the TOF watch is recalibrated. The TOF ratio is normalized to the values obtained during the calibration Procedures. After these steps, the neuromuscular blocking agent is administered according to protocol.

The number of thumb twitches upon electrical stimulation of the ulnar nerve is measured and recorded.

- At 15 seconds intervals, the TOF was measured and in the case of TOF $\frac{1}{4}$ 0, this was followed by the PTC (30 Hz for 5 seconds, 3 seconds later Single twitch at 1 Hz) every 6 minutes. In our study, a TOF of 1–2 reflects a moderate NMB and a PTC of 1–2 reflects a deep NMB. Finally, when four twitches are present in the TOF, the ratio of the fourth to the first twitch was determined (the TOF ratio).
- The stimulation of TOF (2 Hz four stimuli) was changed to every 15 seconds after end of surgery and then measure at 1, 3, 5, 10 minutes after finish the procedures, and at 0, 15, 30, 60, 90 during in PACU.

Neuromuscular data were collected via an interface to a computer by means of the TOF-Watch[®] SX Monitoring Program. TOF Watch[®] SX can also be used in GCP clinical studies. The easy-to-read display presents all relevant data. This data can be simultaneously uploaded, via a fiber-optic connection, to a computer running the TOF-Watch SX Monitor program.

Additional variables:

Additional variables will include duration of surgery, drug dosages (Propofol, fentanyl, muscle relaxant, reversal agent, other agents used during anesthesia), duration from reversal to extubation, ventilatory variables (Tidal volume, respiratory rate, breathing pressure), transfer to ward, to ICU or home.

Hemodynamic variables including heart rate (HR), and mean arterial pressure (MAP) are recorded pre-induction, 60 seconds after fentanyl injection, after applied of Propofol TCI, every minute after tracheal intubation. A HR of <55–60 beat/min is determined as bradycardia which is to be treated with atropine 10 µ/kg. The limit for hypotension is MAP <60 mmHg which is to be treated with the titration of ephedrine intravenously. The incidence of bradycardia or hypotension will be recorded.

Post Operative Residual Curarization Evaluation/Follow – Up:

Residual blockade will be evaluated after extubation in the OR and in the PACU, as well as at post day 1 (TOF Ratio < 0.9 [only in OR and PACU] , pulmonary complication i.e. desaturation <90%, desaturation < 80%, reintubation, aspirate pneumonia, hospital death).

Study measurements in the post-anesthesia care unit In the PACU, the following variables will be measured at 15 min, 30 min, 60 min and 90 min: respiratory rate, arterial oxygen saturation, numerical pain rating (on a scale from 0, no pain, to 10, most severe pain imaginable), bleeding, hoarseness and occurrence of nausea or vomiting.

Before discharging from Post-Operative Care Unit, patients will be assessed “time readiness to discharge from PACU” by evaluating Modified Aldrete recovery score. The score will be measured at least 15 minutes interval.

MODIFIED Aldrete recovery score¹⁴

Parameter	Description of patient	Score
Activity level	Moves all extremities voluntarily/on command	2
	Moves 2 extremities	1
	Cannot move extremities	0
Respirations	Breathes deeply and coughs freely	2
	Is dyspneic, with shallow, limited breathing	1
	Is apneic	0
Circulation (blood pressure)	Is 20 mm Hg > preanesthetic level	2
	Is 20 to 50 mm Hg > preanesthetic level	1
	Is 50 mm Hg > preanesthetic level	0
Consciousness	Is fully awake	2
	Is arousable on calling	1
	Is not responding	0
Oxygen saturation as determined by pulse oximetry	Has level >90% when breathing room air	2
	Requires supplemental oxygen to maintain level >90%	1
	Has level <90% with oxygen supplementation	0

Maximum total score is 10; a score of ≥ 9 is required for discharge.

- Main goals are controlling postoperative pain, controlling nausea and vomiting, and reestablishing normothermia prior to discharge
- Majority of patients can meet discharge criteria within 60 minutes in the PACU, no demonstrable benefit from a mandatory minimum duration of PACU care
- Outpatients who meet the above discharge criteria may be “fast-tracked” to phase 2 recovery, similarly inpatients who meet the same criteria may be transferred directly from the OR to their ward. This is required less extensively monitoring.

Statistical Methods:

All statistical analysis will be performed by STATA or SPSS, depends on availability.

Baseline Patients Characteristics:

We will describe the data distribution of each collected variable. We will characterize subjects in both groups by demographics, comorbidities, clinical characteristics i.e. neuromuscular weakness grading, and distribution of ASA Classification pattern. Categorical variables will be summarized by frequency and percent while continuous variables will be summarized by the mean, median, standard deviation, and range.

Clinical Outcomes:

The data analysis will be based on the intent-to-treat approach. All comparisons will be made using an alpha level of 0.05

1. Primary Efficacy endpoints:

The Proportion of patients who have a surgical conditions score of excellent will be compared between the Moderate NMB and Deep NMB groups using Fisher’s Exact test

2. Secondary outcome

- 1) The proportion of patients who are ready to be discharged from post-operative care, defined as Modified Aldrete's score ≥ 9 , at arrival, 15,30,60, 90 minutes after reach of TOF > 0.9 will be summarized.
- 2) The proportion of patients who are ready to be discharged from the operating room, defined as TOF > 0.9 at time of tracheal extubation, at 1,3,5, 10 minutes after finish of Procedures will be summarized.
- 3) The frequency of patients with clinical signs of early recovery during Endolaryngeal Procedures will be compared between the deep NMB and Moderate NMB arms using Fisher's Exact test.

Clinical signs of early recovery:

- 1) Airway pressure alarm
- 2) Movement of Vocal cords on Laryngeal Video monitor
- 3) Movement of the abdomen
- 4) Change of End Tidal CO₂

Other outcomes:

-

- 1) Proportion of patient at risk of Post-Operative Residual Curarization (PORC) (PORC) (TOF ratio < 0.9) at 1,3,5,10, minutes after finish of Procedures and at arrival ,15,30, 60,90minutes during Post-Operative Care Unit stay.
- 2) Time to ready-to-discharge from Post-operative Care Unit which is time from Post-operative Care Unit (PACU) admission to reach "acceptable" score of Post-operative discharge score.
- 3) Time to ready-to-discharge from operating room, which is time from finish of Procedures to train of Four ratio > 0.9
- 4) Intubating condition in patients who has endotracheal insertion. This will be assessed by anesthesiologist right after finishing intubation by using the same score of endolaryngeal surgical condition

Categorical variables will be compared using the Fisher's exact test while continuous variables will be compared using the student's t-test or Mann-Whitney U test, depending on the sample distribution.

Descriptive will be utilized to describe surgical conditions rating by Anesthesiologists during the Procedures, and VDO Surgical condition scoring by an ENT surgeon and Anesthesiologist. Categorical variables will be summarized by frequency and percent while continuous variables will be summarized by the mean, median, standard deviation, and range.

Descriptive and univariate statistics may be utilized to describe demographics and baseline characteristics of subjects. Multivariate logistic regression analysis may be employed to examine the predictive value of various baseline factors on efficacy endpoints.

Sample size calculation:

The primary outcome's sample size calculation:

Based on data from the BLISS study¹⁵, the proportion of patients a with a score of Excellent on the Surgical Rating Score (SRS) among subjects who receive deep NMB with Rocuronium is approximately 99%, while this proportion for patients who received moderate NMB with atacurium followed by mivacurium was lower (82%)..

By using 80% power and 1-sided $\alpha=0.05$, we performed sample size calculation by using the following formula.

For the proportion outcomes

$$n = \frac{2(\bar{p})(1 - \bar{p})(Z_{\beta} + Z_{\alpha})^2}{(p_1 - p_2)^2}$$

All expected primary outcome, secondary outcomes and calculated sample sizes are shown in the following table

	Deep NMB	Mode rate NMB	Sample size
Primary outcome			80% Power
- Proportion of Excellent	99%	82%	36/arm

Since we expect 13% of withdrawal from the study¹⁶, we need to inflate the total sample size to **80 subjects (40 subjects per arm)**.

As mentioned in the earlier session, the first five Procedures performed in conformance with this protocol will not be used for data analysis; thus, the Procedures will be practiced five times each center before data collection starts.

Therefore, the total enrolled patients are 110 patients.

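### Randomisation is stratified by airway, but the primary Fisher test ignores the stratum: valid, with a small loss of efficiency if airway predicts the score

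*Combined protocol and SAP*

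**What the plan says.** Under Treatment allocation, section 2.5 describes the allocation: "The randomization will be performed by computer-generated block randomization algorithm with allocation concealment". It then adds: "The randomization will be stratified into" two classes, anaesthesia with an endotracheal tube and anaesthesia without one. Airway is the only stratification factor named.

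Under Clinical Outcomes in section 2.7, the primary endpoint "will be compared between the Moderate NMB and Deep NMB groups using Fisher’s Exact test". No stratum enters that test. The analysis set is fixed by "The data analysis will be based on the intent-to-treat approach", and the significance level by "All comparisons will be made using an alpha level of 0.05", without saying whether the test is one- or two-sided. The synopsis likewise names Fisher's exact test for categorical variables.

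The one place where a covariate could enter is optional: "Multivariate logistic regression analysis may be employed to examine the predictive value of various baseline factors on efficacy endpoints". It does not name airway and is not the primary analysis.

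The sample size calculation in section 2.7 begins "By using 80% power and 1-sided" alpha of 0.05, assumes 99% against 82% excellent, and has no stratum term.

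**The concern.** Stratifying the allocation balances the arms on airway. If airway also predicts the score, the pooled test treats the between-stratum difference as noise and becomes more conservative than it need be. The analysis then leaves unused some of the precision the design created.

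The documents give reasons to think airway could matter. The sponsor chose it as the sole stratifier. One of the three score components is the reaction to passing a tube and inflating its cuff. Excellent requires 8 or 9 points of 9, so one component can decide the classification.

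What is at stake is efficiency only. Neither the validity of the primary result nor the stated sample size depends on this point.

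**Working it through.** **1. The plan's own figure.** With p1 = 0.99, p2 = 0.82 and mean 0.905, the formula in section 2.7 gives, one-sided,

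n = 2 × 0.905 × 0.095 × (0.8416 + 1.6449)² / 0.17² = 36.8 per arm.

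The plan states 36, which is also what the usual formula with separate null and alternative variances returns. Two-sided, the plan's formula gives 46.7. So 36 is the one-sided, unstratified figure.

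**2. Inputs for the comparison.**
- From the plan: 99% excellent in the deep arm; 82% overall in the moderate arm; 40 per arm planned; 36 per arm as the calculated size before the 13% withdrawal allowance.
- From the Airway type rows of the characteristics table at the end of the document: 27 + 25 = 52 tube and 17 + 21 = 38 tubeless. 40 × 52/90 = 23.1, so one scenario uses strata of 23 and 17 per arm. The others use equal strata.
- Assumed, because no document gives them: the moderate-arm rate in each stratum, always averaging 82%. For example, (23 × 0.95 + 17 × 0.644)/40 = 0.820. The deep arm is 99% in both strata.

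**3. The two tests.** Both reject at p ≤ 0.05, with no mid-p correction. Two-sided p-values are by probability ordering.
- Pooled Fisher: given the total number rated excellent, the deep-arm count is hypergeometric.
- Exact stratified (Cochran-Mantel-Haenszel type): let S be the deep-arm number rated excellent, summed over strata. Given the total in each stratum, S is distributed as the convolution of the two stratum hypergeometrics. The one-sided p-value is P(S ≥ observed).

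**4. Power, by enumerating every possible table (%, pooled vs stratified).**

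| Per arm (strata) | Moderate-arm rates, % | One-sided | Two-sided |
|---|---|---|---|
| 40 (20/20) | 82 / 82 | 76.8 vs 76.8 | 63.5 vs 64.1 |
| 40 (20/20) | 87 / 77 | 77.0 vs 77.1 | 63.7 vs 65.0 |
| 40 (20/20) | 90 / 74 | 77.2 vs 77.5 | 63.9 vs 66.6 |
| 40 (20/20) | 96 / 68 | 78.3 vs 79.4 | 64.7 vs 72.5 |
| 40 (23/17) | 82 / 82 | 76.8 vs 76.9 | 63.5 vs 64.1 |
| 40 (23/17) | 90 / 71.2 | 77.4 vs 78.3 | 64.0 vs 65.9 |
| 40 (23/17) | 95 / 64.4 | 78.6 vs 81.0 | 65.0 vs 71.0 |
| 36 (18/18) | 82 / 82 | 69.4 vs 69.8 | 54.1 vs 54.8 |
| 36 (18/18) | 87 / 77 | 69.6 vs 70.4 | 54.2 vs 55.8 |
| 36 (18/18) | 90 / 74 | 69.8 vs 71.2 | 54.4 vs 57.4 |
| 36 (18/18) | 96 / 68 | 70.8 vs 74.1 | 54.9 vs 64.1 |

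The stratified test loses power in no row. With 20/20 strata, the two one-sided verdicts differ in 0.04%, 0.13%, 0.29% and 1.14% of trials, from the smallest airway gap to the largest.

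**5. False-positive rate.** With both arms set to the moderate-arm stratum rates, rejection stays below 3% for both tests in every row. At 40 per arm with 20/20 strata, one-sided, pooled Fisher falls from 2.9% to 2.1% as the airway gap grows, while the stratified test stays at 2.6%. That growing conservatism is the inefficiency in question.

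**6. The reported surgical grading.** The Intraoperative outcomes table shows 43/48 against 49/49 clinically acceptable, p = 0.027. Pooled Fisher gives C(48,5)/C(97,5) = 0.0266. It is the same one- and two-sided, because the opposite table (all five failures in the deep arm) is more probable. The printed value therefore matches an unstratified Fisher test. It is for clinically acceptable, not for the primary endpoint of excellent, and no result by airway stratum is shown.

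**The case against.** The strongest reply is that nothing here is an error. The pooled test is valid, the plan never promises a stratified analysis, and the choice is between two sound tests. The gain depends on an airway effect that no document reports. With a 10-point gap in the moderate arm it is about 0.1 points one-sided (77.0 against 77.1 at 40 per arm). Nor does stratifying repair the larger shortfall from 80% power, which is mostly Fisher's own conservatism. All of this stands, and it is why the point is minor.

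A second reply is that the average gain guarantees nothing for this trial. That also stands. If the five not-acceptable results are split across airway strata in every possible way, with the seven Combination patients placed in every possible way, the stratified p-value runs from 0.008 to 0.044 one-sided but reaches 0.058 two-sided. A stratified analysis chosen after seeing results could therefore move a conclusion either way, so it must not replace the planned test.

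A third is that the optional logistic regression leaves room for adjustment. That is only a partial answer: it is neither committed nor tied to airway.

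Finally, the documents do not say which stratum the Combination patients were randomised in. That is true of the documents, but stratified randomisation requires the stratum to be recorded at allocation.

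**Conclusion.** The concern holds and is minor. The design stratifies by airway, and no committed analysis uses it. The planned test is unbiased and does not inflate type I error. Its cost, on the one-sided basis used for sizing, is about 0 to 2.5 points of power at 40 per arm and 0.4 to 3.3 points at 36. If the test is two-sided, which section 2.7 leaves open, the cost is 0.6 to 7.8 points at 40 per arm and 0.7 to 9.2 at 36.

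These ranges rest on assumed stratum rates averaging 82% in the moderate arm, with 99% in both deep-arm strata. The upper ends need a moderate-arm gap of 28 points (96 against 68) or about 31 points (95 against 64.4). Most of the shortfall from 80% power would remain after the change and is a separate matter.

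**What to change.** **In a plan not yet analysed:** in section 2.7, name as the primary test the exact stratified (Cochran-Mantel-Haenszel type) test by airway stratum as randomised, and state whether it is one- or two-sided. Report the Mantel-Haenszel risk difference with its 95% confidence interval and the counts by stratum. Keep pooled Fisher as a sensitivity analysis.

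**In this trial, where results are already shown:** report the planned Fisher test as primary. Add the stratified analysis beside it, labelled post hoc.

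In both cases, use the stratum recorded at randomisation. This follows the intent-to-treat rule and places the 4 + 3 = 7 of 97 patients in the Combination row, whom the two strata do not otherwise define.

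**Cost:** one or two sentences and one extra command, with no added patients or data. The chosen package (STATA or SPSS) must support the exact stratified test, and the gain is close to nothing if airway does not predict the score. If the airway effect is strong, the treatment difference also varies by stratum. At 96/68 it is 99 − 96 = 3 points in one stratum and 99 − 68 = 31 in the other, so a single pooled risk difference should be read with the stratum counts.
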